Hypotheses 2a.1, 2a.2, 2b.1 and 2b.2 initially will be tested using the same mixed model procedure identified in Hypothesis 1a and 1b. To test for mediation effect, we will utilize the analytic strategy described by Krull and MacKinnon (1999, 2001). In this approach, four conditions must be met: a) a significant relationship between the independent variable (treatment) and the dependent variable (PTSD symptoms as measured by CAPS), b) a significant relationship between the independent variable and the proposed mediator (Attention Model: mindfulness and attentional control; Coping Model: tolerance of discomfort and coping), c) a significant relationship between the mediators and the outcome, and d) the relationship between the independent variable and outcome must be significantly lower after controlling for the proposed mediator. The multiple-mediation model includes a multiple-path mediating effect through both mediators (i.e. mindfulness and attentional control or tolerance of discomfort and maladaptive coping), which allows one mediator (e.g., mindfulness) to causally affect the other mediator (e.g., attentional control). Multimodal assessment is used for Attentional Control, Tolerance of Discomfort and Coping based on the theoretical models discussed previously. The relation among these variables and their individual contribution to the construct of interest will be examined in order to

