remove variables or create composites. Correlation coefficients among the outcomes for each mediator will be examined. Furthermore, the main effect of each outcome will be examined in the mixed effect model. Low correlated outcomes or outcomes that are highly (greater than .8) correlated with each other and/or low contribution in the model will be considered to be dropped from the model. The effect of mediators in the model can be calculated based on either the difference between two regression parameters ($\tau - \tau^2$) or the multiplication of two regression parameters ($\alpha\beta$) (MacKinnon, Warsi, & Dwyer, 1995). The variance estimates produced by the various methods are quite similar to each other and to the true value of the variance in situations involving continuous multivariate normal data and a continuous independent variable (MacKinnon et al., 1995). Although there is some evidence that the least model in the case-control study design setting this approach could provide biased estimations for the indirect effects (Wang et al., 2012), we believe the Sobel (1982) procedure to test for significant mediation is most appropriate approach for this study. Next we will use the formula provided by MacKinnon and Dwyer (1993) to determine the percentage of the intervention condition to primary outcome path that was accounted for by change in our mediator. We acknowledge that this method may not be supportable given the need to reduce sample size. If the study biostatistician determines that this is the case, she will utilize other strategies to analyze available data and generate testable hypotheses for future studies. The exploratory aim will be analyzed using similar approach. Data will be analyzed from all randomized subjects on whom we have a baseline assessment and at least one post-baseline evaluation. All statistical tests will be two-tailed. We will adjust p-values for multiple testing as appropriate.

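### The percentage mediated is planned without an interval: at 48 per arm and a medium effect it cannot separate a true 25% from a true 50%, and the four significance conditions inflate small shares

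*Combined protocol and SAP*

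**What the plan says.** The mediation part of the Analytic Plan sets a sequence. It opens with prerequisites: "In this approach, four conditions must be met". These are:

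- (a) "a significant relationship between the independent variable (treatment) and the dependent variable", the latter being CAPS;
- (b) "a significant relationship between the independent variable and the proposed mediator";
- (c) "a significant relationship between the mediators and the outcome";
- (d) "the relationship between the independent variable and outcome must be significantly lower after controlling for the proposed mediator".

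The mediated effect is then calculated as a difference or a product of coefficients. For the test, "we believe the Sobel (1982) procedure to test for significant mediation is most appropriate approach for this study". The next step is a published formula "to determine the percentage of the intervention condition to primary outcome path that was accounted for by change in our mediator".

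No interval, expected size or precision is given for that percentage. The Sample size section covers Aim 1 only. Straight after introducing the percentage, the plan concedes that the method may not hold up now that the sample has been cut, and leaves the biostatistician free to use other, hypothesis-generating strategies. It gives no criterion for that decision and names no replacement.

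**The concern.** The percentage is a ratio: the indirect effect divided by the total effect of yoga versus physical activity on CAPS. With about 96 participants and a medium effect, both parts are poorly estimated. A bare point estimate hides this, and a reader would naturally use it to rank mechanisms.

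Requiring significance first adds a second problem. Condition (a) favours trials that overestimate the denominator. Conditions (b), (c) and (d) favour trials that overestimate the numerator. The percentage that survives need not centre on the truth.

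Aim 2 exists to compare the Attention and Coping Models, and the protocol intends the mechanism findings to shape guidance on teaching yoga for PTSD. A percentage that looks much the same for a weak and a strong mechanism would not serve that aim.

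**Working it through.** **Inputs from the documents.** 48 per arm (Feasibility; Sample size). A between-arm difference of 0.5 SD at the last time point (Sample size). Attrition of up to 20% (Sample size): 96 × 0.8 = 76.8, taken as 76 completers or 38 per arm. Two-sided 0.05 (Analytic Plan).

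**Assumptions.** The documents give no path sizes. The base case is one mediator, one end point, within-arm SDs of 1, an arm-to-mediator effect a = 0.5 SD and no baseline adjustment. With total effect c = 0.5, a true share of 25% means ab = 0.125 and b = 0.25; a true share of 50% means ab = 0.25 and b = 0.5. The percentage is taken as ab/c, because the plan does not reproduce the cited formula. Condition (d) is taken as a significant Sobel test.

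**The plan's own figure.** There is none for the percentage. The nearest is at least 80% power for the primary aim. A plain end-point comparison at 0.5 SD, 48 per arm and no attrition gives 69%.

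**Step 1: the denominator.** SE(c) = √(2/48) = 0.204. A typical 95% interval is 0.5 ± 1.985 × 0.204, or 0.095 to 0.905 SD. The quantity being divided by is known only to within about a factor of ten.

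**Step 2: what the conditions select.** The Sobel statistic is z = ab / √(a²·SE_b² + b²·SE_a²), with SE_a = 0.204 and SE_b ≈ √((1 − b²)/96).

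- True 25%: SE_b ≈ √(0.9375/96) = 0.099. The denominator is √(0.25 × 0.00977 + 0.0625 × 0.04167) = 0.071, so z = 0.125/0.071 = 1.76. This is below 1.96, so a trial that estimates every path exactly right fails, and the trials that pass have mostly overestimated the indirect effect.
- True 50%: SE_b ≈ √(0.75/96) = 0.088. The denominator is √(0.25 × 0.00781 + 0.25 × 0.04167) = 0.111, so z = 0.25/0.111 = 2.25. This is above 1.96, so selection on the numerator is milder and roughly offsets the selection on the denominator by condition (a).

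**Step 3: simulation of the base case, given all four conditions.**

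| | True 25% | True 50% |
|---|---|---|
| Middle 95% of estimates, 48 per arm | 20-67% | 27-90% |
| Median, 48 per arm | about 36% | near 50% |
| Median, 76 completers | about 40% | about 50% |

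The two ranges share everything from 27% to 67%. The true medians differ by 25 points; the reported ones differ by about 14 (50 − 36).

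**Step 4: would an interval separate the two values?** Here b was set at 0.3 or 0.5 with a following from the share, 48 per arm, 0.5 SD, 1,500 simulated trials per setting.

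- Median width of the 95% interval, all trials: 101-118 points (true 25%) and 162-181 points (true 50%).
- Interval excludes the other value, all trials: 19% (true 25%) and 7-12% (true 50%).
- Interval excludes the other value, trials meeting all four conditions: 3-6% (true 25%) and 13-25% (true 50%).
- Trials meeting all four conditions: 278-326 of 1,500, or 19-22% (true 25%); 718-744 of 1,500, or 48-50% (true 50%).

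**Step 5: sensitivity, over all trials.** A baseline-outcome correlation of r leaves outcome variance 1 − r², so r = 0.8 leaves 0.36. The interval excludes the other value in:

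- 36-51% of trials at 0.5 SD with r = 0.8;
- 25-44% at 0.8 SD (taken as large) with no adjustment;
- 65-87% at 0.8 SD with r = 0.8.

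**The case against.** **The plan already doubts the method.** This is true and should be credited, and the fallback is framed as hypothesis-generating. But with no criterion and no named alternative, the percentage remains the default output and the choice is left to judgement at analysis.

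**The percentage is not the plan's only measure.** This also stands. The indirect effect is calculated and tested first, and the Background judges the models by comparing fit with single-mediator versions. A reader might infer that the percentage alone would drive the practice guidelines; the documents do not say so. What is missing is an interval and reporting by route.

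**A reader might infer a downward bias**, because a significant total effect selects large denominators. Under condition (a) alone the median does generally fall, in the Step 4 settings to 41-44% for a true 50% and 21-24% for a true 25%. But the plan requires four conditions, and together they push a small share up and leave a 50% share about where it is.

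**A reader might also infer that impossible values are likely.** Without any filter, a true 50% gives estimates from about 11% to 153% in the base case, and with 76 completers 8-13% of estimates fall outside 0-100%. Once all four conditions hold, at most about 1% do. The unfiltered figures apply only if the percentage is calculated regardless of the conditions, in which case it is less precise still.

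**The routes may not be pooled.** The plan recognises a path through both mediators, and the cited formula is not shown. The wording does not establish that routes will be combined; it only fails to say that they will be reported separately.

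**Conclusion.** The point holds for imprecision and for distortion by selection, with the direction of the distortion depending on the true share. At 0.5 SD and 48 per arm, estimates that pass all four conditions run about 20-67% for a true 25% and 27-90% for a true 50%. The median for a true 25% is inflated by about 11 points (15 with 76 completers), and a true 50% is nearly unbiased. The percentage therefore cannot rank a weak mechanism against a strong one at the effect size the plan defines.

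This rests on assumed path sizes and on a single-mediator, single-end-point simplification of the planned mixed and two-mediator models. It does not support saying that the percentage is uninformative in every case. Pilot Effect Sizes speaks of a medium to large effect, and at 0.8 SD with a baseline-outcome correlation of 0.8 the two values are separated in most trials. The matter concerns a secondary aim and leaves the primary comparison untouched.

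**What to change.** Amend the mediation text of the Analytic Plan as follows.

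1. For every mediator, report the specific indirect effect in CAPS points and in SD units, with a bootstrap or Monte Carlo 95% interval, whether or not the total effect or any other condition is significant.
2. In each two-mediator chain, report the three routes separately: through the first mediator only, through the second only, and through both in sequence.
3. If a percentage is still wanted, give it only with its interval and label it descriptive.
4. Name this as the defined analysis at the reduced sample size, in place of the open-ended fallback.

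This uses data already being collected. It costs SAP wording and slightly more analysis work, and there will be no single headline percentage. It will not make the estimates precise, but it will show how imprecise they are and remove the selection.

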Accordingly, the **primary aim** of this randomized clinical trial is to examine the efficacy of a manualized hatha yoga protocol as compared to a supportive physical activity control in a sample of Veterans with PTSD, thus adding to the evidence base in this understudied area. The proposed study incorporates "gold standard" requirements for PTSD treatment trials, including clearly defined target symptoms; reliable and valid measures; use of blind evaluation of outcome; systematic assessor training; manualized, replicable, specific treatment programs; unbiased assignment to condition; and measurement of treatment adherence (Foa & Meadows, 1997). The larger published and ongoing trials of yoga have used wait list, group health education and psychotherapy as control conditions, but none have addressed the important question of whether or not yoga confers more benefit than other types of physical activity; this project answers that need. The yoga literature continues to develop, with recent work showing positive clinical effects when applying Trauma Sensitive Yoga for women (Kelly et al., 2021). This project will contribute to the literature by examining a more typical hatha yoga practice in a diverse sample.

A **secondary aim** of this project is to understand the mechanisms by which clinical change may occur when Veterans with PTSD practice yoga. *This aspect of the study extends our current knowledge as there is no comprehensive model of yoga's impact on PTSD.* Out of this understanding, we envision developing guidelines for the therapeutic application of yoga. Given the tens of thousands of people teaching yoga (Bachman, 2015) and the wide range of settings in which Veterans may practice, trying to disseminate a particular protocol may be infeasible. More realistically, we would aim to extend current trauma-sensitive yoga

[figure not shown]
guidelines, which focus largely on the acceptability of the practice (Emerson, Sharma, Chaudhry, & Turner, 2009), to highlight key principles and postures that support recovery. In doing so, we could create a consumer's guide for yoga for PTSD so that Veterans can apply yoga to work on key concepts wherever they choose to practice. *In doing so, we would greatly enhance the disseminability of effective yoga practice.* Further, we believe that this work has the potential to inform the application of yoga to other mental health conditions, as the mechanisms we propose to examine have applicability to other disorders.

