attrition. It's generalizability to Veterans is also unknown. The other relatively large randomized evaluation of yoga included 64 women with chronic, treatment-resistant PTSD (van der Kolk et al., 2014). As compared to a health-education class, yoga was associated with greater change in PTSD symptoms (Cohen's $d = 1.07$). It is unknown, however, how these findings generalize to men. One uncontrolled trial involved Kripalu yoga, a form of hatha yoga, for active duty and Veteran participants. They observed large effect size pre-post change in symptoms (Cohen's $d = .77$), although this change was less than a benchmark that the authors calculated based on meta-analysis of published studies of active PTSD treatments (Johnston et al., 2015). In contrast, smaller studies have found no difference between yoga and a control condition (Mitchell et al., 2014; Thordardottir et al., 2014) or negligible effect on PTSD symptoms in Veterans ($n = 12$; Staples et al., 2013). Weighting the larger studies more heavily, we have powered the study to detect a medium to large effect size.

Ongoing Research

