conditioning. Each exercise can be modified to meet the needs of individual participants. The classes will be conducted by certified personal trainers. This control group was selected because of its past use as a control condition for Hatha yoga. This type of exercise program was comparable to Hatha yoga in terms of gains in functional fitness (Gothe & McAuley, 2016) but less effective at improving cognition (Gothe, Kramer, & McAuley, 2014) in community-dwelling samples of older adults.

Analytic Plan

Descriptive statistics will be obtained for all variables, including distributions, means, medians, variances, standard deviations, skewness, kurtosis, ranges, and quartiles. Tests of normality of continuous measures will be made using the Shapiro-Wilk W and the Kolomogorov D statistics in conjunction with plots of the distribution of data and descriptive measurements. The data will also be examined for homogeneity of variance. An appropriate statistical method will be employed to correct for any abnormalities. Missing data values will be minimized by intensive training of the assessors in techniques of clarifying answers and checking questionnaires while participants are on-site. When missing values are identified, we will employ several approaches to reduce their influences. If at all possible, participants will be rescheduled or a telephone call will be made within 24 hours of completion of tests or interviews. The pattern of missing data will be examined according to the procedure recommended by Little and Rubin (1987), which includes comparing group differences in the primary outcomes of subjects with versus without missing data. We will also test whether the drop-outs are random or systematic by comparing the drop-outs with the study completers on the baseline data. An absence of significant differences would support the random nature of drop-outs. Effect of drop-outs will be minimized by including all subjects in the analyses and by including any effect of systematic differences between the drop-outs and completers in the model as a covariate when applicable.

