Each outcome variable will be graphed versus time for each subject for all available time points (baseline, mid-treatment, post-treatment, follow-up) to evaluate what function of time best describes the data. Hypotheses 1a and 1b will be tested using the Mixed Effect Model (Hedeker, Gibbons, & Waternaux, 1999). This method is robust with respect to drop-out and missing data. These mixed models allow us to assess whether important estimates are dependent on missing data patterns, and provide overall estimates of effects by averaging over the various missing-data patterns (Hedeker et al., 1999). In addition, we will use the extension of the Pattern-Mixture Models (Guo, Ratcliffe and Ten Have, 2004), which allows subject-to-subject heterogeneity and assess if there is bias due to drop out or missing data. The Mixed Effect method has several advantages over more traditional analytic approaches such as a change score, end-point or repeated measures analysis of variance. It allows the inclusion of subjects with missing data or those who were terminated early in the study, without relying on data imputation procedures. This method provides an estimate of the individual variability around the population trend, the variability of the individual intercepts (baseline values) and slopes (changes across time), and the correlation between them. We will include a random intercept, a random effect for assessment time, and fixed effects for comparison groups and group-by-time interaction in the model. A fully saturated treatment by time model will be utilized for inference. Co-variance structure will be chosen based on Akaike's Information Criterion (AIC). Random group level treatment effects will also be evaluated for importance based on the model AIC. This allows for any group level effects to be incorporated into the model. Denominator degrees of freedom will be calculated using the Kenward-Roger small sample correction. Statistical significance will be determined by $p < .05$ for hypothesis 1a and $p < .01$ (.05/5 to correct for multiple comparisons) for hypothesis 1b.

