Sample size. We used the method provided by Hedeker, Gibbons, & Waternaux (1999) for the Random Regression Model and the RMASS program provided by Hedeker (2016) to estimate needed sample size for Aim 1. Medium effect size was selected based on finding from previous yoga trials (Wells et al., 2016) and was defined as a between-group difference increasing linearly from 0 at baseline to .5 SD units at the last time point. The minimum power estimation is based on sample size calculation for 10% and 20% attrition, correlations of 0.2, 0.5, and 0.8 between the repeated measures, and for medium and large effect sizes. We are confident that with the proposed total sample size of at least 48/arm would be sufficient to achieve a minimum 80% power for the primary aim.

Management

Management of this single-site study will be [name] responsibility. She has considerable experience in research management from small developmental grants (e.g., NCCIH R34) to a large multi-site consortium (INTRuST PTSD/TBI Clinical Consortium Deputy Director) and center of excellence (VASDHS CESAMH Associate Director). Administrative aspects of the project will be supported by [name], who has been [name] lead coordinator for more than a decade. [name] will coordinate scientific aspects of the project, holding regular meetings with the investigative team. [name], the study biostatistician, will work closely with [name] around data management and analysis. [name] will draw on his experience with yoga research to help with issues of recruitment, enrollment and retention. Drs. [name] (attention) and [name] (pain) will provide guidance in their relative areas of expertise. [name], who is a licensed clinical psychologist, also will be responsible for clinical oversight. The timeline of major study activities is presented in Table 2.

Table 2. Study Timeline

Year 1 (2018-2019)	Year 2 (2019-2020)	Year 3 (2020-2021)	Year 4 (2021-2022)	Year 5 (2022-2023)
Original Timeline				

Set-up	Recruitment (approx. 6/month x 30 mos)	Follow-up, data lock	Dissemination	Analyses	
Regulatory	Assessment				
Hiring	Intervention delivery, fidelity (12 groups)				
Training	Data management				
Recruitment	DSMB reporting				
Revised Timeline					

 ✓ Set-up ✓ Regulatory 	
 Recruitment (approx. 6/month x 30 mos) Assessment Intervention delivery, fidelity (12 groups) Data management DSMB reporting 	Follow-up, data lock	Dissemination	Analyses	

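### At 48 per arm, 80% is not the minimum power for 0.5 SD on the plan's own grid, and 0.5 SD has no stated support against an exercise control

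*Combined protocol and SAP*

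**What the plan says.** The primary aim compares hatha yoga with a supportive physical activity class on CAPS total score. The Sample size paragraph gives the basis for the effect ("Medium effect size was selected based on finding from previous yoga trials (Wells et al., 2016") and defines it as "a between-group difference increasing linearly from 0 at baseline to .5 SD units at the last time point". It lists a grid of 10% and 20% attrition, correlations of 0.2, 0.5 and 0.8, and medium and large effects. It concludes that at least 48 per arm is "sufficient to achieve a minimum 80% power for the primary aim".

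The Pilot Effect Sizes section describes the target differently: "Weighting the larger studies more heavily, we have powered the study to detect a medium to large effect size". The effects it reports are 1.65 against a wait list, 1.07 against a health-education class, and 0.77 as an uncontrolled pre-post change. It also mentions smaller studies with no difference or a negligible effect, and it gives a literature range of 0.08 to 1.65.

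On comparators, Background and Significance says: "The larger published and ongoing trials of yoga have used wait list, group health education and psychotherapy as control conditions". It adds that none of these trials asked whether yoga does better than other physical activity. The only yoga-versus-exercise data cited are in older adults, on fitness and cognition. On fitness, the Physical activity section says: "This type of exercise program was comparable to Hatha yoga in terms of gains in functional fitness". On cognition, exercise did less well than yoga. Neither outcome is PTSD.

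**The concern.** The control here is a weekly exercise class matched to yoga on class time, home practice, group contact and expectancy. A difference seen against a wait list, or a change seen with no control, need not carry over to that contrast. The plan draws its effect from a literature whose larger trials, by its own account, never tested the contrast, and it does not say what allowance was made.

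That would matter less if 48 per arm left ample room at 0.5 SD. So the question is whether the 80% is a floor across the stated grid. If it is not, readers will rely on a figure that is true in only part of the grid. Aim 2 is also affected, because the mediation strategy first requires a significant treatment effect on CAPS.

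**Working it through.** **Inputs from the protocol.** 48 per arm (Feasibility; Sample size). Difference of 0.5 SD at the last time point. Correlations 0.2, 0.5, 0.8 and attrition 10%, 20% (Sample size). CAPS at baseline, post-treatment and follow-up, so three visits (Table 1). Alpha: "Statistical significance will be determined by $p < .05$ for hypothesis 1a". Sidedness: "All statistical tests will be two-tailed". The model has a saturated group-by-time mean (Analytic Plan).

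**Assumptions not in the protocol.** Compound symmetry; half the attrition before post-treatment and half before follow-up; a normal approximation; 0.8 SD as the meaning of a large effect.

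**Step 1, no attrition.** The contrast is the group difference in change from baseline to last visit. In SD units its standard error is SE = √[4(1 − r)/n], and power = Φ(d/SE − 1.96). With n = 48 and d = 0.5:

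- r = 0.2: SE = √(3.2/48) = 0.258; Φ(1.936 − 1.960) = 49%
- r = 0.5: SE = √(2.0/48) = 0.204; Φ(2.449 − 1.960) = 69%
- r = 0.8: SE = √(0.8/48) = 0.129; Φ(3.873 − 1.960) = 97%

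Two of the three correlations miss 80% before any attrition.

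**Step 2, with attrition.** Generalized least squares uses all observed visits: SE = √(c′(Σ n_p X_p′V_p⁻¹X_p)⁻¹c), summed over arms and dropout patterns p. Here V has 1 on the diagonal and r elsewhere, and c picks out the same contrast. The smallest difference detectable with 80% power is (1.960 + 0.842) × SE. Power is in percent.

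| r | Attrition | SE | 0.2 SD | 0.3 SD | 0.4 SD | 0.5 SD | Detectable at 80% |
|---|---|---|---|---|---|---|---|
| 0.2 | 10% | 0.2665 | 11 | 20 | 32 | 47 | 0.747 SD |
| 0.2 | 20% | 0.2766 | 11 | 19 | 30 | 44 | 0.775 SD |
| 0.5 | 10% | 0.2120 | 15 | 29 | 47 | 65 | 0.594 SD |
| 0.5 | 20% | 0.2214 | 15 | 27 | 44 | 62 | 0.620 SD |
| 0.8 | 10% | 0.1348 | 32 | 60 | 84 | 96 | 0.378 SD |
| 0.8 | 20% | 0.1414 | 29 | 56 | 81 | 94 | 0.396 SD |

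Example, r = 0.5 and 20% attrition: 0.5/0.2214 = 2.258; Φ(2.258 − 1.960) = Φ(0.298) = 62%.

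The plan's minimum of 80% at 0.5 SD is therefore not reproduced. It needs a correlation of about 0.65 (10% attrition) to 0.68 (20%).

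**Step 3, sensitivity at 0.5 SD.** A linear-trend test gives the same figures to within a percentage point. Other settings, at r = 0.2, 0.5 and 0.8 across the two attrition rates:

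- Four time points, linear trend: 48–51%, 67–70%, 96–98%.
- Linear trend with a common baseline: 67–71%, 74–78%, 96–97%.
- First-order autoregressive covariance: lower in every cell, and 0.765 to 0.796 at r = 0.8.
- One-sided test (contrary to the plan), linear trend: 57–59%, 73–76%, 97–98%.

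None makes 80% a minimum.

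**Step 4, the comparator.** 0.5/1.07 = 47% and 0.5/1.65 = 30%, so the planning value is already well below both controlled effects. The protocol does not say why, and it gives no PTSD effect for yoga against exercise from which to judge the reduction.

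**The case against.** **0.5 SD may already be cautious.** It is below every PTSD effect size the protocol attaches to a named study, and it is defined as the difference between the two arms of this trial. A reader might infer that the stated power is overstated because exercise supplies part of the benefit. For example, removing one-third of 0.5 SD leaves 0.33 SD, and power falls to 22–24%, 32–34% and 65–69%. The documents do not support that step. They never present 0.5 SD as the effect against a non-exercise control, and they give no share for exercise. The same one-third or one-half taken off 1.07 leaves 0.71 or 0.54 SD, both above 0.5. This objection stands. It does not, however, supply a justification for 0.5 SD: the cited range starts at 0.08, the controls in the smaller null studies are not named, and the review cited for the effect cannot be checked here.

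**The minimum may refer to the large effect.** If large means 0.8 SD, the worst cell gives 82% to 85%, which fits the claim. But the paragraph says the medium effect was selected, and the 80% statement is not limited to the large one.

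**A null is not bound to happen or to be misread.** A reader might also infer that non-significance is the likely result, or that it would be taken to mean that the meditative component is inactive. Neither follows in general. At r = 0.8 a true 0.33 SD is detected more often than not, and the protocol states the question without planning that reading.

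**It is late.** The document dates from August 2022, after 38 months of active recruitment, and 48 per arm was set by accrual. That stands, and it limits the remedy to wording and reporting.

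**Conclusion.** The point holds in two parts. First, 0.5 SD has no stated support for yoga versus exercise. That is a gap in justification, not evidence that the value is too large. Second, and more firmly, 80% is not the minimum power at 48 per arm for 0.5 SD: the figures are about 44–47%, 62–65% and 94–96% at correlations of 0.2, 0.5 and 0.8. Taken together, if the true difference against exercise is smaller than planned, only the high-correlation cells have any margin. There, 0.4 SD keeps 81–84% power, but 0.3 SD has 56–60%.

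The exact percentages rest on the covariance structure and dropout pattern assumed above. The failure of 80% as a minimum does not, since it persists in every variant tried at 0.5 SD.

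**What to change.** In the Sample size paragraph:

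- Replace the single 80% statement with power at 48 per arm for 0.2, 0.3, 0.4 and 0.5 SD at each planned correlation and attrition rate. State the number of CAPS visits and the covariance structure used.
- Give the smallest difference detectable with 80% power: about 0.38–0.40, 0.59–0.62 and 0.75–0.78 SD at correlations of 0.8, 0.5 and 0.2.
- State that no yoga-versus-exercise estimate for PTSD was available, and give the reason for choosing 0.5 SD.
- Reconcile the medium effect here with the medium-to-large target in Pilot Effect Sizes.

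In the Analytic Plan, commit to reporting the yoga-minus-exercise CAPS difference with its 95% confidence interval. From the SEs above, 1.96 × SE gives half-widths of about 0.26–0.28, 0.42–0.43 and 0.52–0.54 SD at correlations of 0.8, 0.5 and 0.2. A fixed cut-off for calling a result inconclusive is not advised: the protocol supports no particular value, and with intervals this wide a small cut-off such as 0.3 SD would catch nearly every non-significant result.

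The cost is a few sentences and one table, with no added patients or visits. The downside is that the stated power becomes less favourable.
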